## **Protocol**

To complete the aims and objectives of this project we are planning a pilot randomized, double blinded, placebo controlled clinical trial of nitric oxide added to the sweep gas of the oxygenator during cardiac surgery requiring CPB in infants.

Inclusion Criteria: Infants less than one year of age undergoing cardiac surgery with the use of cardiopulmonary bypass.

Exclusion Criteria: Prior surgery requiring CPB within the same hospitalization, pre-operative need for ECMO or mechanical circulatory support, known hypersensitivity to nitric oxide, known hemostatic or thrombotic disorder that results in an altered transfusion/anticoagulation protocol

Equitable subject selection: All patients will be considered for eligibility that meet the inclusion/exclusion criteria regardless of race, gender, or ethnic background. Non-English speaking patients will be considered for inclusion if a suitable consent form can be approved prior to their surgical procedure. A Spanish language short form will be submitted along with the initial study as we anticipate some eligible subjects will be Spanish speaking only. Other languages encountered in eligible patients will be considered on an individual basis and if a suitable consent form can be drafted and approved prior to the patient's surgical date, they will be considered for enrolment.

Sample Size: 40 patients equally distributed amongst the treatment and placebo groups

Power Calculation: using 0.05 as type 1 error tolerance and previous data from neonatal CPB studies, a minimum sample size of 12 patients is necessary to detect a difference of a change in platelet count (Specific Aim 1) of 50 with a power of 91%.

Sample size justification: In order to maximize the ability to estimate a sample size for a larger multi-institutional trial (Specific Aim 2) we need to maximize the number of patients enrolled within this local pilot trial. Approximately 120 infants annually meet the inclusion/exclusion requirements annually at CHW. Given experience with prior interventional studies in this population, we anticipate a consent rate of approximately 33%. Therefore we anticipate being able to enroll 40 patients into this trial within one year.

Randomization: Stratified to insure the number of patients with Society of Thoracic Surgery (STS) Mortality Class 1-3 and 4-5 surgeries are equally distributed.

Justification for stratification of randomization: The complexity of congenital cardiac surgery is known to significantly impact morbidity and mortality (16). In order to insure an equal distribution of patients with this known confounder among groups we will stratify the randomization to insure an equal distribution to active and placebo groups.

Recruitment: The PI and co-investigators have access to the cardiac surgical scheduling coordinators. We will be in contact with them and browse the list of scheduled surgical patients at the weekly surgical conference. The PI and co-investigators are also active clinicians within the cardiac intensive care unit and will be looking for eligible patients amongst the census of the intensive care unit within the normal course of their clinical duties. No fliers or published materials will be used. If the patient has an identified primary cardiologist at the time they are deemed to be eligible, we will contact them prior to approaching the patient/family to answer any questions they would have.

Treatment: A minimum sweep gas flow of 2.5 L/min will be used in all patients with CO2 added to maintain PaCO2 35-40 mmHg. All patients will have an INOmax DSIR device in line with the sweep gas. Nitric oxide at a dose of 20 ppm will be added to the sweep gas of the treatment group from the initiation to the conclusion of CPB. The placebo group will not receive nitric oxide but will be connected to the INOmax DSIR device.

The INOmax DSIR device and nitric oxide will be supplied by Mallinckrodt Pharmaceuticals. A letter indicating this support from Mallinckrodt is included in the package.

Blinding: All care providers involved in the clinical care of the patient will be blinded to treatment group (and methemoglobin levels) for 30 days post-operatively or hospital discharge (whichever is later). A single study staff (perfusionist or respiratory care practitioner) will be responsible for nitric oxide delivery according to the randomization scheme outlined above.

Study Measurements (Primary objectives in **bold**):

Aim 1:

Baseline and at conclusion of cardiac repair/prior to transfusion: **Change in platelet count**, platelet response to TRAP, U46619, and CRP (to be done at the Blood Research Institute)

Aim 2:

**30 day (all cause) mortality, length of hospital stay post-operatively**, transfusion volumes of platelets and pRBCs, total number of transfused products, length of mechanical ventilation post-operatively, vasoactive infusion score (highest within the first 24 hours post-operatively), need for ECMO within 48 hours post-operatively, and total hospital cost.

Aim 3:

Baseline, at conclusion of CPB, and upon arrival to ICU: **Methemoglobin levels**

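### ICU-arrival methemoglobin may not isolate the bypass exposure: nitric oxide by other routes is not named for recording, and the Aim 3 comparison names no time point or baseline

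*Combined protocol and SAP*

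**What the plan says.** **Treatment (Protocol).** In the treatment arm nitric oxide "will be added to the sweep gas of the treatment group from the initiation to the conclusion of CPB". For the control arm: "The placebo group will not receive nitric oxide but will be connected to the INOmax DS" device. Both statements stand in the paragraph on the sweep gas.

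**Eligibility (Protocol).** Inclusion reads "Infants less than one year of age undergoing cardiac surgery with the use of cardiopulmonary bypass". The exclusions mention nitric oxide only as hypersensitivity: "known hypersensitivity to nitric oxide, known hemostatic or thrombotic disorder that results in an altered transfusion/anticoagulation protocol". Current inhaled nitric oxide is not addressed. Recruitment draws partly on infants already in intensive care, since the investigators "will be looking for eligible patients amongst the census of the intensive care unit within the normal course of their clinical duties".

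**Blinding (Protocol).** "All care providers involved in the clinical care of the patient will be blinded to treatment group (and methemoglobin levels"), for 30 days after surgery or until discharge, whichever is later.

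**Study Measurements, Aim 3 (Protocol).** Methemoglobin is in bold, the plan's mark for a primary objective. It is taken "Baseline, at conclusion of CPB, and upon arrival to ICU".

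**Statistical Analysis Plan.** Methemoglobin levels are among the continuous variables to be compared by t-test or Mann-Whitney test. The plan does not say which of the three samples is compared, or whether the baseline sample is used. The examples of confounders for regression are surgical complexity, age, gender, race, ethnicity, weight and genetic disorder.

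**The concern.** Aim 3 needs a methemoglobin contrast that can be attributed to nitric oxide in the bypass circuit. Study delivery stops when bypass ends, but one of the three samples is taken later, at ICU arrival. Nothing in the plan prevents clinical nitric oxide from being started in between, and nothing names it as a data item.

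Because that use would begin after randomization, randomization does not guarantee that it is balanced between arms. If it differs by arm, the ICU-arrival difference mixes the circuit exposure with the later one. Without recorded times, a raised value at that sample could not be assigned to either source once the trial is over. An analysis that names no time point also leaves open which of three different questions the primary Aim 3 test answers.

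**Working it through.** **Plan's own figure.** The documents give no effect size, standard deviation or rate for methemoglobin, so there is nothing to reproduce for Aim 3. The only power statement concerns platelet count.

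**What each planned methemoglobin sample can contain.**

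| Sample | Circuit nitric oxide | Other-route use before surgery | Other-route use started between bypass and ICU |
|---|---|---|---|
| Baseline | no | yes | no |
| Conclusion of CPB | yes, treated arm | yes, partly accounted for by baseline | no |
| ICU arrival | yes, whatever persists | yes, partly accounted for by baseline | yes, either arm |

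The middle sample, read against baseline, is the one closest to the circuit exposure. The ICU-arrival sample is the one open to later use.

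**Can the control-arm sentence be read as a bar on all routes?** It covers one arm only, stands in the sweep-gas paragraph and gives no route or period. Care providers do not know the arm, so they could not apply a placebo-only bar on clinical use. The workable reading is that it governs the sweep gas.

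**Effect on the ICU-arrival contrast.** Let *a* be the mean methemoglobin rise from circuit nitric oxide still present at ICU arrival, and *b* the mean rise from other-route nitric oxide. Let *pT* and *pP* be the proportions of treated and placebo infants on other-route nitric oxide at that sample.

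- If the two rises add: observed difference = *a* + *b*(*pT* − *pP*). With *pT* = *pP* the second term is zero and the mean difference is unchanged. With 40 infants split equally, there are 20 per arm, so one extra exposed infant in one arm contributes 1/20 = 0.05 × *b*. The sign depends on which arm has more use.
- If the two rises are equal and do not add: every treated infant has *a* and a fraction *pP* of placebo infants also has *a*. Observed difference = *a*(1 − *pP*). For assumed *pP* of 5%, 10%, 20% and 30%, this is 95%, 90%, 80% and 70% of *a*.

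The proportions in the second case are a range for illustration, not estimates. None of *a*, *b*, *pT* or *pP* is in the documents.

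**Side check on Aim 1.** Suppose pre-operative inhaled nitric oxide acted exactly like the circuit exposure in 5–10% of placebo infants. A platelet difference of 50 would become 50 × 0.95 = 47.5 or 50 × 0.90 = 45. The plan's standard deviation is not stated. Back-solving from its difference of 50, 91% power and alpha 0.05 (two-sided t-test assumed) gives 35.4 if the 12 patients are per arm, or 23.6 if 12 is the total of both arms. At 20 per arm and SD 35.4, power is 99% for 50 and 97% for 45. At SD 23.6 it is close to 100% for both.

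**The case against.** **The plan already holds a sample that isolates the bypass exposure.** True: the conclusion-of-CPB sample comes before any nitric oxide started on the way to the ICU. This narrows the point but does not remove it, because the analysis section does not say that this sample is the one compared.

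**ICU-arrival methemoglobin by assigned arm, under usual care, is a legitimate safety comparison.** This also stands, and it is why the sample should be kept. It answers a different question from the effect of circuit nitric oxide alone.

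**The data fields may exist.** The REDCap database is described only in general terms and no field list is given, and the confounder list is offered as examples. The supportable statement is that other-route nitric oxide is not named, not that it will go unrecorded.

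**Stronger readings that the documents do not support.**

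- A reader might infer that the platelet endpoint is diluted. That requires pre-operative inhaled nitric oxide to act on the change across bypass as circuit nitric oxide does, which no section says. Pre-operative use is balanced on average by randomization. The second platelet sample is taken at the end of the repair, ahead of transfusion, so nitric oxide started after bypass does not reach it. Even on the unfavourable assumption above, the loss is about 2 points of power.
- A reader might infer a bias towards no harm, because infants given circuit nitric oxide might need less of it later. No section says so, and the difference could move either way.
- A reader might conclude that infants already on inhaled nitric oxide should be excluded. That is an eligibility trade-off for the sponsor. Accrual has no slack: 120 × 0.33 = 39.6 a year against a target of 40. Losing an assumed 5–10% would leave 37.6 to 35.6.

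**Conclusion.** The gap is real but confined to Aim 3. The plan controls nitric oxide in the sweep gas during bypass only and does not name other-route use as a data item or covariate. It leaves the methemoglobin comparison without a time point or baseline. The ICU-arrival contrast may therefore fail to isolate the bypass exposure.

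Neither the size nor the direction can be stated. Both depend on how often other-route nitric oxide is used in each arm and how far it raises methemoglobin. If use were equal and effects additive, the mean difference would not shift at all. The conclusion rests on two readings of the text: that the control-arm sentence governs the sweep gas, and that no other-route field is planned beyond what is written. The change is worth making because it is cheap and the missing times may not be reliably recoverable afterwards.

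**What to change.** 1. In the Statistical Analysis Plan, name the between-arm comparison of conclusion-of-CPB methemoglobin, adjusted for the baseline value (or as change from baseline), as the primary Aim 3 contrast.
2. Add REDCap fields for nitric oxide by any route other than the study circuit, with start and stop times, running from before the baseline sample to at least ICU arrival.
3. Keep ICU-arrival methemoglobin as a secondary safety comparison by assigned arm, and report the number in each arm on other-route nitric oxide at that sample. Any split of results by that use is descriptive only, because the use is post-randomization and the subgroups are not randomized comparisons.
4. Have the sponsor state which route and period the control-arm sentence covers, and whether infants already on inhaled nitric oxide are eligible. No eligibility or clinical-use rule is proposed here.

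**Cost.** A few data fields and a few lines of text, with no new blood sample. The downside is that ICU-arrival methemoglobin moves from one of three undifferentiated primary time points to a secondary one.

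### The blind expires infant by infant, so most earlier allocations may be released while the recruiting clinicians are still enrolling

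*Combined protocol and SAP*

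**What the plan says.** The Blinding paragraph is the only rule on the blind. It applies to "All care providers involved in the clinical care of the patient", who "will be blinded to treatment group (and methemoglobin levels) for 30 days post-operatively or hospital discharge (whichever is later". One staff member, a perfusionist or respiratory care practitioner, delivers the gas and necessarily knows the arm.

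Three other parts of the Protocol bear on this:

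- Recruitment: "The PI and co-investigators are also active clinicians within the cardiac intensive care unit and will be looking for eligible patients". The recruiters are therefore among the care providers whose blind lapses.
- Sample size justification: "Therefore we anticipate being able to enroll 40 patients into this trial within one year".
- Sample Size and Randomization: "40 patients equally distributed amongst the treatment and placebo groups", stratified by STS mortality class (1-3 against 4-5). No block size or method of concealment is given.

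Nothing in the Protocol or the Statistical Analysis Plan ties the end of the blind to the end of enrolment, last follow-up or database lock. The SAP has no planned interim look and no rule on who may see data by arm.

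**The concern.** A blind that ends a fixed time after each operation protects that infant's outcomes. It does not protect the trial while enrolment continues. Once the first few infants pass their limit, nothing in the plan prevents the recruiting clinicians from learning their arms and methemoglobin values.

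Three things are then at stake:

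- Selection and consent. Clinicians who know how earlier infants fared by arm may change whom they approach, when, and how they present the trial. About one family in three is expected to consent, so there is room for this. Known past allocations can also carry some information about the next one when arms are balanced within strata.
- Care of later infants. Transfusion volumes, length of ventilation and vasoactive score are secondary measures under Aim 2 that depend partly on decisions by the same clinicians. So does post-operative stay, which is marked as a primary objective of that aim.
- Informal looks by arm. With 40 infants and mortality among the objectives, a few events in infants of known arm could sway a decision to continue, with no plan governing it.

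**Working it through.** **Inputs from the Protocol.** 120 eligible infants a year; consent about 33%; 40 infants, 1:1; one year of enrolment; blind of at least 30 days per infant.

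**Assumptions.** Accrual is even, surgery is on the day of enrolment, and all infants share a common blind length W. The minimum W is 30 days. Longer values stand for later discharge, because the documents give no length of stay.

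**Step 1: the plan's accrual figure.** 120 × 0.33 = 39.6, and 120 × 1/3 = 40. The stated 40 in one year reproduces.

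**Step 2: spacing.** d = 365/40 = 9.125 days between enrolments.

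**Step 3: earlier infants past the blind.** At the k-th enrolment, infant j is past the blind if (k − j) × d ≥ W, that is, if k − j ≥ c, where c is W/d rounded up. The number past the blind is k − c (zero if k ≤ c). For W = 30, 30/9.125 = 3.29, so c = 4 and the count at the 40th enrolment is 40 − 4 = 36.

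**Step 4: when this becomes most earlier infants.** More than half are past the blind when k − c > (k − 1)/2, which gives k ≥ 2c.

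| W (days) | c | Past the blind at 40th enrolment | Share of 39 | More than half from enrolment |
|---|---|---|---|---|
| 30 | 4 | 36 | 92% | 8 |
| 45 | 5 | 35 | 90% | 10 |
| 60 | 7 | 33 | 85% | 14 |
| 90 | 10 | 30 | 77% | 20 |
| 120 | 14 | 26 | 67% | 28 |
| 180 | 20 | 20 | 51% | 40 |

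At W = 30, more than half of the earlier infants are past the blind at 40 − 8 + 1 = 33 of the 40 enrolments. At W = 60 this is so at 27, and at W = 90 at 21.

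**Step 5: random accrual and variable stay.** A simulation used 1,500 trials per scenario, 40 infants enrolled uniformly over 365 days, two equal strata, and lognormal stay with median 10 to 30 days and log-SD 0.7. Release was at the later of day 30 and discharge. About 34 to 36 of the 39 earlier infants were releasable at the last enrolment, and 66% to 73% of earlier infants on average over enrolment.

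**Step 6: predictability.** In the same simulation, with permuted blocks of 2, 4 or 6 and a recruiter who knows every releasable code, the next allocation was certain for 4% to 9% of infants. The best guess was right 53% to 58% of the time, against 50% by chance. The documents state neither the use of blocks nor a block size, so these figures are illustrative only.

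**Step 7: what the per-infant window covers.** Study Measurements places platelet count and function at baseline and at the end of repair before transfusion, and methemoglobin at baseline, end of bypass and ICU arrival. Vasoactive score is taken within 24 hours, ECMO need within 48 hours, mortality at 30 days, and stay runs to discharge. All fall within the later of 30 days and discharge.

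**The case against.** The strongest reply is that the text fixes how long the blind lasts and does not say that anyone is told anything afterwards. That stands. A reader might infer that the investigators would watch platelet, methemoglobin and mortality results build up by arm. The documents do not support this: they describe no release of codes, no circulation of results by arm, and nobody pairing codes with outcomes. The counts above are of releasable infants, not released ones.

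A second reply is that the rule keeps each infant's own care providers blind while that infant's outcomes arise. That also stands, so it would be wrong to read this as unblinded assessment of outcomes. The platelet change is a laboratory value taken before the transfusion decisions that might shift, and 30-day mortality is objective. A later infant's own arm stays hidden from its care providers, so care tailored to the arm would need a guess.

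Third, a reader might infer that allocations become readily predictable. The simulated gain is small and depends on assumed blocks and full disclosure, so concealment is weakened only modestly.

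What the replies do not answer is that the stated end date authorises release during enrolment, to a group that includes the recruiters, and that no other provision closes the gap.

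**Conclusion.** The concern holds as a defect in the stated rule. A trial described as double blinded ends its blind infant by infant during about a year of enrolment, and the recruiters are among those unblinded. By the last enrolment most earlier infants are releasable for every blind length examined, from 36 of 39 at 30 days to 20 of 39 at 180 days, where it only just holds. For shorter stays this is true through most of enrolment. The counts rest on even accrual and an assumed length of stay.

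The consequence is a risk to the selection, consent and care of later infants and an opening for informal looks. It bears mainly on clinician-influenced secondary outcomes and little on the platelet endpoint. Whether any release would occur, and how far it would shift any result, cannot be determined from the documents. The change is still worth making, because it is cheap and the pilot is meant to inform a larger trial.

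**What to change.** Replace the per-infant expiry in the Blinding paragraph with:

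> Care providers, the PI and co-investigators, other than the designated staff member who delivers nitric oxide and any person designated for safety review, remain blinded to treatment group and study methemoglobin values until the last enrolled infant has completed follow-up and the database is locked. An individual code or value is released earlier only for that infant's safety, and each release is logged.

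The two exemptions are needed: the operator must know the arm, and the wording must not shut off access to methemoglobin values for safety. The documents name no safety reviewer, so the sponsor would have to say who, if anyone, holds that role.

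With this wording, none of the 39 earlier allocations is routinely releasable when the 40th infant is enrolled. Sample size, treatment and measurements do not change. The cost is that families and clinicians of early infants wait up to about a year longer to learn the allocation.

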### **Statistical Analysis Plan**

A redcap database will be created to collect all data fields and insure data integrity. Statistical support will be through a qualified statistician from the Clinical and Translational Science Institute of Southeast Wisconsin, [name]. We plan to compare continuous variables such as change in platelet count; platelet response to TRAP, U46619, and CRP; length of stay; length of mechanical ventilation; transfusion volumes; total hospital cost; and methemoglobin levels with either a Mann Whitney test or t-test. A chi-square analysis will be used for dichotomous variables such as mortality and need for ECMO. Multivariate or regression analysis will be done as needed to control for significant cofounders such as surgical complexity scoring, age, gender, race, ethnicity, weight, and presence of known genetic disorder.

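### The Aim 1 primary is an unadjusted raw change in platelet count, so size-dependent dilution by the circuit prime adds avoidable variance that a pre-specified covariate would remove

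*Combined protocol and SAP*

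**What the plan says.** Under Study Measurements in the Protocol, the Aim 1 laboratory measures are "Change in platelet count, platelet response to TRAP, U46619, and CRP", of which only the platelet-count change is bolded as primary. The sampling times are "Baseline and at conclusion of cardiac repair/prior to transfusion". Aim 3 uses different times, "Baseline, at conclusion of CPB, and upon arrival to ICU", so the end of bypass is named there as its own time point.

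The eligible population is "Infants less than one year of age undergoing cardiac surgery with the use of cardiopulmonary bypass". Forty infants are split equally between arms, and randomisation is stratified by STS mortality class (1-3 against 4-5), not by weight or age.

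The Power Calculation states that "a minimum sample size of 12 patients is necessary to detect a difference of a change in platelet count" of 50 with 91% power, "using 0.05 as type 1 error tolerance and previous data from neonatal CPB studies". It gives no SD.

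The Statistical Analysis Plan says "We plan to compare continuous variables such as change in platelet count" with a two-group t-test or Mann-Whitney test. Regression is left to be used where it seems necessary. Its candidate covariates include weight, age and surgical complexity, but neither baseline platelet count nor prime volume. No prime volume, haematocrit, percentage change or dilution-corrected count appears in either part of the document.

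**The concern.** When an infant's blood mixes with the prime, the platelet count falls even if no platelet is lost. The size of that fall depends on prime volume relative to blood volume, and so largely on weight, and it is proportional to the baseline count. The raw change therefore adds together platelet loss, which nitric oxide might reduce, and dilution, which it cannot affect.

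The cost is precision. This is the only outcome with a power calculation. A nuisance component that is largely predictable from facts known before treatment starts is left in the error term. With 20 per arm and no stratification by size, a chance difference in weight or baseline count between arms can also look like platelets gained or lost.

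**Working it through.** **The plan's own figure.** The 91% power cannot be reproduced because no SD is given. Solving backwards with a two-sided t-test at 0.05 and a difference of 50, the SD would have to be 23.6 if 12 is the total (6 per arm) or 35.4 if 12 is per arm. The document does not say which.

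**Dilution in one infant.** All dilution inputs are assumptions, since the documents give none. The formula is: expected fall = baseline count × prime/(blood volume + prime). With blood volume 85 mL/kg and baseline count 300:
- 3 kg, prime 300 mL: 300 × 300/(255 + 300) = 162
- 8 kg, prime 350 mL: 300 × 350/(680 + 350) = 102

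That is (162 − 102)/5 = 12 per kg. A chance difference of 1 kg in mean weight between arms would shift the comparison by roughly 12.

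**Spread between infants.** Take weight lognormal with median 4.5 kg, blood volume 82 mL/kg, prime about 200-400 mL and baseline count 300 with SD 80. Dilution alone then has an SD of about 41-46, or about 24-25 with the baseline count held at 300. Both size and baseline count therefore contribute. Other assumed weight, prime and baseline distributions gave 26-50, and 20-26 at a fixed baseline.

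**Standard error with 20 per arm.** For the unadjusted comparison, SE = √(2/20) × √(dilution SD² + residual SD²).
- Residual SD 30: 0.316 × √(41² + 30²) = 16.1; 0.316 × √(46² + 30²) = 17.4
- Residual SD 60: 0.316 × √(41² + 60²) = 23.0; 0.316 × √(46² + 60²) = 23.9

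If the dilution term were fully explained, the floors would be 0.316 × 30 = 9.5 and 0.316 × 60 = 19.0. Estimating the covariate slopes raises these slightly. Simulation at residual SD 30 gives:

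| Analysis | SE of treatment effect |
|---|---|
| Raw change, unadjusted | about 16-17 |
| Adjusted for baseline count | 12-13 |
| Baseline count and weight | 10.1-10.3 |
| Baseline count and predicted dilution | 9.6-9.9 |

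Taking mid-range values, adding predicted dilution to baseline count cuts the variance by 1 − (9.75/12.5)² = 39%. Adding weight instead cuts it by 1 − (10.2/12.5)² = 33%. At residual SD 60 the cut from predicted dilution beyond baseline count is only about 7-15%.

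**What this means for power.** Take 50 as the difference seen in the diluted samples. With 20 per arm, two-sided power is about 87% at a total SD of 50, 73% at 60 and 54% at 75. The unadjusted total SDs above are 0.316 into 16.1-17.4, or about 51-55, at residual SD 30, and about 73-76 at residual SD 60. Adjustment brings these close to 30 (power above 99%) and 60.

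**Chance imbalance.** The SD of the arm difference due to dilution alone is 0.316 × 41 to 46, or about 13 to 14.5. In simulation it exceeded 15 in 26-31% of trials. That figure includes the part arising from baseline count.

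**The case against.** The strongest reply is that dilution acts in both arms, so randomisation already deals with it. That stands as far as bias goes. A reader might infer that dilution hides any platelet-sparing effect, and the documents do not support that. It adds noise, and under some assumed inputs the raw comparison keeps high power.

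A reader might also set the 60-point gap between a 3 kg and an 8 kg infant against the difference of 50. The first is a gap between two individuals and the second a difference between arm means. Dilution would produce a 60-point shift only if mean weight differed by about 5 kg between arms.

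Several further points stand:
- Weight and age are already named as possible covariates, and weight with baseline count recovers most of the gain. What is missing is a commitment to adjust, together with baseline count and prime volume.
- The SD behind the 91% came from neonatal bypass studies and may already include some dilution noise. It cannot be said that the power calculation ignored dilution, only that the trial enrols infants of a wider size range than neonates.
- Sampling after mixing with the prime is inferred, not stated. Even so, a sample just before or just after bypass ends would be diluted.
- Subtracting an expected count does not restore a sparing effect that is itself diluted. With an assumed mean retained fraction of 0.53-0.75, 50 on the undiluted scale appears as 50 × 0.53 to 0.75, about 27-38, in both the raw and the adjusted analysis. The gain is in variance only.

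**Conclusion.** The concern holds as a matter of efficiency and chance imbalance, not bias. The plan's primary comparison leaves a size-dependent nuisance component in the error, and nothing commits the analyst to removing it. Under the stated assumptions, the standard error falls from about 16-24 to about 10-20. The gain is large if residual variation is near SD 30 and modest if it is near 60. Part of it comes from baseline count and most of the rest from weight; recorded prime volume adds a little more.

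The size of the gain rests on assumed blood volume, prime volume, weight distribution, baseline count and residual SD, and on a platelet-free prime. The share of the fall that is dilution cannot be calculated from the documents.

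**What to change.** Make the primary Aim 1 analysis a pre-specified linear regression of the change in platelet count on treatment, baseline platelet count and expected dilution fall. Define that fall as baseline count × prime volume/(blood volume + prime volume), with blood volume taken from pre-operative weight at one fixed mL/kg figure. If prime volume is not recorded, use weight in its place. Keep the raw change by arm as a secondary presentation. State whether the second Aim 1 sample is drawn before or after bypass ends, and give the SD behind the 91% power.

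Weight and prime volume are set independently of arm, before nitric oxide starts, so adjusting for them adds no post-randomisation bias. The cost is one extra REDCap field and a few sentences of SAP text, with no extra sample or patient. The downside is reliance on a standard blood-volume estimate and a platelet-free prime. Because the regression estimates the slope, errors in these mainly cost precision; they do not bias the randomised comparison.

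### Transfusion volumes have no stated unit and are compared without planned weight adjustment in infants up to one year old, which costs precision if volume rises with weight

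*Combined protocol and SAP*

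**What the plan says.** Under Study Measurements, Aim 2, the protocol lists "transfusion volumes of platelets and pRBCs, total number of transfused products". No unit is given, neither mL nor mL/kg. The section is headed "Study Measurements (Primary objectives in" bold type. In Aim 2 the bold items are 30-day mortality and post-operative hospital stay, so transfusion volume is not a primary objective.

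The Statistical Analysis Plan compares "transfusion volumes; total hospital cost; and methemoglobin levels with either a Mann Whitney test or t-test". Neither test adjusts for anything. It then adds: "Multivariate or regression analysis will be done as needed to control for significant cofounders such as surgical complexity scoring, age, gender, race, ethnicity, weight". Weight is therefore a named covariate, but no trigger, model or outcome is attached to it.

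Three design facts matter here:

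- Eligibility is "Infants less than one year of age undergoing cardiac surgery with the use of cardiopulmonary bypass", with no weight limits.
- The sample is "40 patients equally distributed amongst the treatment and placebo groups", that is, 20 per arm.
- Randomisation is "Stratified to insure the number of patients with Society of Thoracic Surgery (STS) Mortality Class 1-3 and 4-5 surgeries are equally distributed". Neither weight nor age is a stratification factor.

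**The concern.** A newborn and an infant close to one year old differ greatly in size. If the volume transfused goes up with body size, part of the spread in recorded volumes reflects weight and not transfusion need. With 20 per arm and no balancing on weight, the arms will also differ somewhat in mean weight by chance. An unadjusted test leaves all of this in the error term.

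The regression sentence does not settle the matter. It applies only where adjustment is judged necessary, names several covariates for 40 patients, and does not say that transfusion volume will be among the adjusted outcomes. Weight could be left out, or brought in after the data have been seen.

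Transfusion volume is clinically close to the platelet hypothesis of Aim 1, and the sample size justification ties Aim 2 to sizing a larger trial. The documents do not say that the transfusion-volume SD will be used for that sizing. If it were, the SD would partly reflect this centre's mix of weights.

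**Working it through.** **The plan's own figure.** None is given for transfusion volume. The only power statement (12 patients, a difference of 50 in platelet count change, 91% power) concerns another outcome. It cannot be reproduced because no SD is stated, and it has no bearing here.

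**Inputs.** From the documents: 20 per arm. Assumed, because the documents give no weights or volumes: weight CV (CVw) 0.3-0.4 and CV of volume per kg (CVk) 0.5-1.0.

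**Step 1: chance difference in mean weight.** The standard error, as a fraction of mean weight, is CVw × √(2/20).

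- CVw 0.3: 0.3 × 0.316 = 9.5%; × 1.96 = ±19%.
- CVw 0.4: 0.4 × 0.316 = 12.6%; × 1.96 = ±25%.

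These are the edges of a 95% range. If volume is proportional to weight, mean volume shifts by the same percentage. This is the same weight variation that enters step 2, so the two must not be added together.

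**Step 2: precision lost if volume is proportional to weight.** On the log scale, with weight and per-kg volume independent, the ratio of unadjusted to weight-free variance is [ln(1+CVk²) + ln(1+CVw²)] / ln(1+CVk²).

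- Mildest case, CVk 1.0 and CVw 0.3: (0.693 + 0.086) / 0.693 = 1.12; 40 / 1.12 ≈ 36.
- Strongest case, CVk 0.5 and CVw 0.4: (0.223 + 0.148) / 0.223 = 1.67; 40 / 1.67 ≈ 24.

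Weight's share of the log-variance is 1 − 1/ratio, about 11% to 40%.

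**Step 3: dependence on how volume scales with weight.** Simulation with 20 per arm, lognormal data, 4,000 runs, volume = k × weight^b, CVw 0.4, CVk 0.5 and a 40% reduction in volume. Power of the Mann-Whitney test:

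| Scaling b | Unindexed volume | mL/kg |
|---|---|---|
| 1 (proportional) | 0.70 | 0.90 |
| 0.5 | 0.85 | 0.86 |
| 0 (unrelated) | 0.90 | 0.72 |

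A weight-adjusted rank or log analysis gave 0.87-0.92 under all three scalings. Ordinary linear regression on untransformed weight gave 0.84 at b = 1.

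**Step 4: false-positive rate.** With no treatment effect (CVw 0.4, CVk 0.75, b = 0 and 1), rejection rates were 4.3% to 5.2% for the Mann-Whitney and t-tests on unindexed and per-kg volume and for regression on weight.

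**The case against.** The strongest objection is that the plan never says volumes will be compared in plain mL. It is silent on the unit, and indexing by weight is as compatible with the text as not indexing. That stands. A reader might infer that raw volumes are planned, but the documents support only an unstated unit together with an unadjusted test.

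A reader might also infer that weight would swamp a key outcome. The documents mark other Aim 2 measures as primary, and weight is a minority of the variance in every setting tried. Nor does a chance weight imbalance produce spurious findings at more than the nominal rate. Randomisation puts that imbalance into the test's standard error, as step 4 shows.

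Two further objections have force. First, the plan already names weight as a covariate, and adjustment recovers most of the loss. This is correct, but the plan does not commit to using it, and that commitment is what is missing. Second, mL/kg is not reliably better. It gains if volume is proportional to weight, makes no difference at b = 0.5, and loses if volume is unrelated to weight, as might happen if products are given in fixed amounts. The documents do not say which applies. This objection defeats a remedy based on mL/kg alone but not one based on weight adjustment.

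Finally, weight should be available at analysis, so nothing irreversible is lost. That limits the importance of the point without removing it.

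**Conclusion.** The point holds as a minor one. As written, the plan's main comparison of transfusion volumes does not use weight, and any adjustment is left open. If volume is proportional to weight, with CVw 0.3-0.4 and CVk 0.5-1.0, 40 patients give the precision of about 24-36. The loss shrinks as the dependence on weight weakens and disappears if there is none. The CVs and the scaling are assumptions. The false-positive rate is not affected, and the outcome is not a primary objective.

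The conclusion that does not depend on the unknown scaling is that a weight-adjusted analysis holds its power under every scaling tried, while the unindexed test and the mL/kg test each lose power under one of them.

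**What to change.** In the Statistical Analysis Plan, replace the unadjusted test with discretionary adjustment, for transfusion volumes, by a prespecified weight-adjusted main analysis. One suitable form is a rank-based ANCOVA of volume on treatment, weight and STS stratum. If there are no zero volumes, regression of log volume on treatment, log weight and STS stratum is an alternative. The stratum belongs in the model because the randomisation is already stratified on it.

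In Study Measurements, Aim 2, state the unit and report volumes as mL per kg of weight at surgery as the descriptive summary. Do not rely on mL/kg as the only correction.

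The cost is one or two degrees of freedom (weight and stratum) and slightly more analysis work. No new data item is needed, since weight and surgical complexity are already named as covariates.
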